3.1 Data source

The data for this study will be retrospectively abstracted from medical charts of eligible patients with PROS at participating clinical sites and treated with alpelisib. Physician narratives will also be generated based on information recorded in the patients' medical charts and will be entered in the eCRF.

A CRF completion guide will be developed and training related to data entry will be completed for each site personnel, so that chart abstraction for the eCRF is conducted in accordance with the study protocol. A detailed data monitoring document will be developed and data will be reviewed with queries raised through the EDC platform for each site to address.

Information entered into the eCRF will be linked to available MRI scans, CT scans, clinical photographs, or clinical videos using a unique study patient ID. The unique patient ID will be automatically generated.

Novartis Data Management or designated CRO will assure database quality processes are followed including review of the data entered into the CRFs by investigational staff for completeness and accuracy, and in accordance with the data validation plan.

All analyses will be performed by Novartis, and/or a designated CRO. SAS version 9.4 or later software will be used to perform all data analyses and to generate tables, figures and listings.

3.2 Analysis population(s)

The **full study population** will include all patients that satisfy the study inclusion criteria. This population set will be used for all secondary [REDACTED] efficacy analyses and for safety analyses.

The **efficacy population** is a subset of the full study population, which will be used for the analysis of the primary endpoint and includes patients who meet the following criteria:

- Patient had at least one target lesion
- Patient had an imaging scan performed on the index date (or up to 24 weeks prior to the index date) for at least one target lesion

3.3 Key post index date time points for reporting endpoint over time.

Considering the retrospective nature of the study, patients might have data available at different time-points. In order to maximize the use of data abstracted, key time points and associated time windows are identified for reporting purpose. For each of these time-points or intervals all patients with data available will be used. The total number of patients in a time interval will be equal to the number of patients with at least one valid assessment in that specific time window. The number of patients (N) in each interval will be summarized in the disposition table and used throughout the report. Only the time points with data available for at least 10% of the patients will be displayed in the corresponding output.

Key study time points are summarized in [Table 3-1](#).

Table 3-1 Time windows for post-index date key-time point

Key time-points	Allowed windows
4 weeks	Up to 10 weeks
12 weeks	[10 to 20 weeks[
24 weeks*	[20 to 32 weeks[
36 weeks	[32 to 40 weeks[
52 weeks	[40 to 58 weeks[
End of study	4 weeks prior to and up to min(study treatment discontinuation + 30 days, cut-off date)

* 24 weeks or 6 months (+/- 4 weeks).

After week 52 intervals of approximately 11 weeks (e.g. 63 weeks, 74 weeks, etc.) with a time window of +/- 5 weeks will be used until the "end of study".

Week 24 windows (+/- 4 weeks) is intended to include assessments performed 24 weeks or 6 months after index date, where 6 months is approximated to week 27.

The last interval, referred to as "end of study" in [Table 3-1](#), will include data available within the last 4 weeks prior to study treatment discontinuation plus 30 days or cut-off date, whichever comes first. When a patient discontinues data will be reported in the "end of study" time window as well as the one corresponding to the assessment (e.g., a patient discontinued treatment at week 58 data will be reported in the key point 52 weeks interval and in the "end of study").

In instances where more than one measure is reported in the time window associated with a key time-point (e.g., at 12 weeks), the measurement taken closest to the key-time point will be considered in the analysis. If two measures were taken on dates that are equidistant from the key time-point (e.g., 12 weeks - 5 days and 12 weeks + 5 days following the index date), the measure associated with a more severe condition (e.g., larger non-target lesion volume, higher pain severity score, lower functional assessment score) will be considered.

In instances where both a non-missing value and a missing or unknown value are reported in the time window associated with a key time-point, only the non-missing value will be considered in the analysis.

Similar rules applies to the volumetric measurement available for the patients.

If a patient has more than one volumetric measurement available for a single target lesion in the time window associated with the index date (i.e., up to 24 weeks prior to the index date) or at 24 weeks (i.e., ± 4 weeks) following the index date, the measurement taken closest to the index date or 24 weeks following the index date will be considered in the analysis. If two volumetric measurements for a single target lesion were taken on dates that are equidistant from the index date or 24 weeks following the index date, the larger of the two measurements (i.e., greatest volume) will be considered. All measurements available will be listed.

Imputation rules for the dates are reported in the [Appendix](#).

3.4 Patient disposition, demographics and other baseline characteristics

Patient disposition

All patients in the MAP will be screened to identify the eligible patients and the number (%) of patients included in the Full study population set will be presented. The number (%) of patients in the Full study population who are still on treatment at the time of the cutoff date, patients who discontinued and the reason for discontinuation will be presented overall and at key time-points.

The number (%) of patients in each analysis set (defined in [Section 3.2](#)) will be summarized overall and at key time-points.

Protocol deviation summaries

The number and percentage of patients in the Full study population with any protocol deviation will be summarized by deviation category. All protocol deviations will be listed.

Demographic and clinical characteristics at index date

All demographic and clinical characteristics information collected at index date and during the pre-index period will be summarized and listed based on the full population set.

Descriptive analyses will be conducted where categorical data (e.g. sex, age groups, ethnicity, PRO subtype, PI3KCA mutation, mosaicism proportion, presence/absence of target and non-target lesions, site of lesions) will be summarized by frequency counts and percentages; the number and percentage of patients with missing data at index date will be provided. Continuous

data (e.g. age, number of lesions) will be summarized by descriptive statistics (N, mean, median, standard deviation, Q1, Q3, minimum and maximum).

Non-medical resource use (e.g., physical therapy, occupational therapy, home care services), frequency of hospitalizations and ER visits, proportion of patients receiving prior PROS-related medication during the pre-index period will be summarized and listed. Prior PROS medications and PROS-related surgical/vascular interventions will be reported since diagnosis, where available.

Separate summaries will be presented for ongoing and historical medical conditions. The summaries will be presented by primary system organ class (SOC) and preferred term (PT). Medical history, comorbidities and current medical conditions will be coded using the Medical Dictionary for Regulatory Activities (MedDRA) terminology. The latest available MedDRA version at the time of the analyses will be used. The MedDRA version used for reporting will be specified in the CSR and as a footnote in the applicable tables/listings.

All other data collected during the pre-index period and at index date will be listed based on their availability.

3.5 Primary endpoint

The primary endpoint will be the proportion of patients with response (yes/no) at Week 24 or 6 months (+/- 4 weeks), defined by achieving at least 20% reduction from index date in the sum of measurable target lesion volume (1 to 3 lesions, via central review of imaging scans), provided that none of the individual target lesions have $\geq 20\%$ increase from index date and in absence of progression of non-target lesions and without new lesions. The primary endpoint measure is summarized in [Table 3-2](#).

Patients who permanently discontinue alpelisib prior to 24 weeks of treatment, patients who required surgery as rescue therapy between index date and 24 weeks of treatment and patients with MRI scan performed at Week 24 or 6 months for which the volumetric measurement cannot be calculated are defined as non-responders.

The primary analysis will be performed on all patients in the efficacy population without missing response (complete case analysis).

3.5.1 Definition of response

Patients included in the analysis population for the primary endpoint will be defined as responders if they meet the following criterion:

- Patient achieved $\geq 20\%$ reduction from index date (or up to 24 weeks prior) in the sum of target lesion volumes (1 to 3 lesions, via central radiological assessment) by the change between the index date and 24 weeks or 6 months (+/- 4 weeks) following the index date
- None of the individual target lesions has $\geq 20\%$ increase from index date to Week 24 or 6 months (+/- 4 weeks)
- Patient did not permanently discontinue alpelisib prior to 24 weeks of treatment

- Patient did not require surgery as rescue therapy between index date and 24 weeks of treatment with alpelisib due to disease deterioration
- No progression of non-target lesions at Week 24 or 6 months (+/- 4 weeks)
- No appearance of new lesions at Week 24 or 6 months (+/- 4 weeks)

Patients will be defined as non-responders if they meet at least one of the following criteria:

- Patient achieved < 20% reduction from index date (or up to 24 weeks prior) in the sum of target lesion volumes (1 to 3 lesions, via central radiological assessment) by the change between the index date and 24 weeks or 6 months (+/- 4 weeks) following the index date
- Any of the individual target lesions has $\geq 20\%$ increase from index date to Week 24 or 6 months (+/- 4 weeks)
- Patient permanently discontinued alpelisib prior to 24 weeks of treatment
- Patient require surgery as rescue therapy between index date and 24 weeks of treatment with alpelisib due to disease deterioration.
- Progression of non-target lesions at week 24 or 6 months (+/- 4 weeks)
- Appearance of new lesion at week 24 or 6 months (+/- 4 weeks)
- Patients with MRI scan performed at week 24 or 6 months (+/- 4 weeks) for which the volumetric measurement of the selected target lesions (1 to 3 lesions, via central radiological assessment) cannot be calculated.

Patients will be considered as having a missing response if lesion volume(s) assessment at 24 weeks or 6 months (+/- 4 weeks) following the index date is not available and:

- Patient did not permanently discontinue alpelisib prior to 24 weeks of treatment and
- Patient did not require surgery as rescue therapy between index date and 24 weeks of treatment with alpelisib due to disease deterioration.

All patients in the efficacy population without a missing response will be used for the primary analysis of the primary endpoint (complete case analysis).

Surgery as rescue therapy is considered as required due to worsening of any existing lesions or development of a new lesions requiring intervention while on alpelisib treatment.

Disease progression at any assessment is defined as an increase of any individual target lesions of $\geq 20\%$ in volume from previous assessment, progression of non-target PROS lesions or appearance of a new PROS lesion.

Progression based on non-target and new lesions will be based on radiological assessment of the central reader.

In relation to non-target lesions, progression will be assessed for the lesions that are identified at index date (or up to 24 weeks prior) with available information at Week 24 or 6 months (+/- 4 weeks) and new lesions. At Week 24 the central imaging reviewer will make a conclusion if overall level of non-target disease burden decreased or increased unequivocally.

Evaluation of radiographic response and progression of all measurable lesions (target and non-target) will be provide to Novartis by a third party vendor. All details are summarized in the Independent Central Review Charter (ICRC).

Table 3-3 Primary endpoint measure

Measure	Type of variable	Statistics	Time point for reporting
Proportion of patients with response at Week 24 provided that none of the individual target lesions have $\geq 20\%$ increase from index date and in absence of progression of non-target lesions and without new lesions	Binary	n, missing, frequency, percentage, 95% CI	At 24 weeks (6 months)

The primary analysis for this study will be descriptive in nature (estimation based), and therefore no hypothesis testing will be conducted. Categorical and binary data will be presented by frequency counts and percentages. The Clopper-Pearson exact method will be used to estimate 95% CIs for binary data.

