#### **Analysis population(s)**

The **full study population** will include all patients that satisfy the study inclusion criteria.

The **efficacy population** is a subset of the full study population, which will be used for the analysis of the primary endpoint and includes patients who meet the following criteria:

- Patient had at least one target lesion.
- Patient had an imaging scan performed on the index date (or up to 12 weeks prior to the index date) for at least one target lesion.

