- Truly non-measurable lesions (for example, superficial visual lesions, masses, organomegaly, PROS-related enlargement of anatomic area identified by physical exam that is not measurable by reproducible imaging technique)
- Definition of new lesion will be detailed in the in the Independent Central Review Charter.

2 Changes to the protocol specified analysis

The following update on time windows were implemented following outcome of internal audit conducted in early Jan 2021.

The time window was extended for the baseline imaging scans to include imaging scans performed up to 24 weeks prior to index date, instead of 12 weeks as indicated in the protocol, to allow for flexibility given the retrospective/real world nature of the EPIK-P1 study. The extension to the time window is intended to reflect the majority of the local medical practice and to include the maximum number of patients for the primary analysis. Furthermore, the extension to the time window is unlikely to modify the baseline assessment significantly as there is not published evidence that the disease may spontaneously improve.

The time window was extended for the 24 weeks scan to include imaging scan assessments between 20 weeks and 31 weeks for the primary endpoint as well as other endpoints, instead of 20 to 28 weeks as reported in the protocol. In accordance with clinical practice in the real world setting, some physicians conducted the imaging scan assessments at 6 months (corresponding to ~ 27 weeks). As such the time window was extended (24 weeks or 6 months +/-4 weeks) to estimate the 24 week endpoints efficiently.

3 Data analysis information

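### Only rescue surgery between index and 24 weeks rules out a response, and no visible analysis shows how many responses follow other volume-reducing procedures done between the two scans

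*SAP*

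**What the plan says.** **Response rule.** Protocol 6.8.1 and SAP 3.5.1 list the criteria for response. The only one about procedures is "Patient did not require surgery as rescue therapy between index date and 24 weeks of treatment with alpelisib due to disease deterioration". SAP 3.5.1 then explains rescue surgery as surgery needed because existing lesions worsen or because of "development of a new lesions requiring intervention while on alpelisib treatment".

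**Scans compared.** The protocol accepted a baseline "imaging scan performed on the index date (or up to 12 weeks prior to the index date"), with a Week 24 window of 20 to under 28 weeks (Table 6-1). SAP 3.2 now accepts an "imaging scan performed on the index date (or up to 24 weeks prior to the index date"). SAP section 2 extends the later window to "include imaging scan assessments between 20 weeks and 31 weeks for the primary endpoint", and Table 3-1 gives 20 to under 32 weeks. If several volumes are available, SAP 3.3 says "the measurement taken closest to the index date or 24 weeks following the index date will be considered in the analysis".

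**Procedures in usual care.** The background sections of both documents (Protocol 4, SAP 1.1) name debulking, amputation, sclerotherapy, laser treatment and endovascular occlusion as current treatment. Protocol 6.3.2 collects surgeries with their intended site, and sclerotherapy and occlusive procedures as non-drug treatment.

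**Planned outputs.** SAP 3.4 reports earlier surgical and vascular interventions since diagnosis where available, and lists other pre-index data. SAP 3.6 (objective #5) tabulates surgery and non-drug treatment over the whole study period in the full population. SAP 3.5.3 has two sensitivity analyses: multiple imputation, and best and worst case. Both apply to patients with missing response. The SAP 3.5.4 subgroups do not include procedures.

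**Imaging rules held elsewhere.** On radiographic evaluation, SAP 3.5.1 states "All details are summarized in the Independent Central Review Charter (ICRC").

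**The concern.** The primary result is a single-arm proportion based on change in lesion volume between two scans. A procedure that removes or shrinks a target lesion between those scans changes the same quantity that is credited to alpelisib, and there is no comparator in which the effect would cancel. The rule removes one such procedure type over one part of the interval. Three routes stay open:

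1. A procedure between the baseline scan and index. This is possible only in patients not scanned again before index, because the measurement closest to index is used.
2. A procedure after 24 weeks but before the later scan.
3. A non-rescue procedure at any time between the scans.

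The other criteria (permanent discontinuation, target-lesion growth, non-target progression, new lesions, volume that cannot be calculated) do not by themselves remove a volume loss caused by a planned procedure. SAP section 2 defends the wider baseline window on the ground that the disease is not known to regress by itself. That speaks to natural history, not to intervention. At stake is whether a reader can separate responses on alpelisib alone from responses that also had a volume-reducing procedure.

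**Working it through.** **1. The plan's own precision figures.** Inputs: n=50 and the response rates in Protocol Table 6-2. Clopper-Pearson limits: lower = Beta(0.025; x, n−x+1), upper = Beta(0.975; x+1, n−x). For x = 10, 15, 20 and 25 of 50 these give 0.1003–0.3372, 0.1786–0.4461, 0.2641–0.5482 and 0.3553–0.6447. All agree with Table 6-2 to rounding.

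**2. Time outside the rescue-surgery rule.** The rule covers 24 weeks. Longest possible interval = baseline window + upper limit of the Week 24 window.

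- SAP (3.2, Table 3-1): 24 + 32 = 56 weeks; 56 − 24 = 32 outside; 32/56 = 57%.
- Protocol (6.8.1, Table 6-1): 12 + 28 = 40 weeks; 40 − 24 = 16 outside; 16/40 = 40%.

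The upper limits are open, so read these as just under 56 and 40. They are ceilings on exposure time for the most widely spaced scan pair, not estimates of bias. A pair taken on index and at exactly Week 24 is fully covered in time, though only for rescue surgery.

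**3. Weight of one patient.** 100/50 = 2.0 percentage points at the protocol's planning size. If missing scans left 30 evaluable patients (an assumption), 100/30 = 3.3 points.

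**4. Illustration at n=50.** The documents do not give the number k of responders affected; k = 1, 3 and 5 are assumed. Starting rates are two rows of Table 6-2.

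| k reclassified | From 15/50 | From 20/50 |
|---|---|---|
| 0 | 30% (17.9–44.6) | 40% (26.4–54.8) |
| 1 | 28% (16.2–42.5) | 38% (24.7–52.8) |
| 3 | 24% (13.1–38.2) | 34% (21.2–48.8) |
| 5 | 20% (10.0–33.7) | 30% (17.9–44.6) |

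**5. Whether a planned output supplies k.** The objective #5 tables cover everyone in the full population up to the end of the study period. They therefore include patients who are not evaluable for response and procedures done after the later scan, and they are not split by response. The pre-index reporting reaches back to diagnosis, well before the baseline scan. Together they bound k from above, loosely. The protocol's narratives (6.3, Patient journey) describe procedures and target-lesion changes patient by patient but yield no rate. The SAP's aim under objective #5 of linking efficacy with clinical benefit specifies no cross-tabulation of response by procedure.

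**The case against.** **The existing outputs may be enough.** If very few patients had any procedure, the tables and listings would settle the matter. That is fair, and it is why the gap concerns the number affected between the scans, not a total absence of procedure data. If procedures are common, as the background sections suggest they could be, the bound is too loose to help.

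**Treated lesions may be dealt with elsewhere.** The Central Review Charter and the Central Imaging Site Manual are not among the documents, and parts of the SAP are redacted. How a resected or sclerosed lesion is read is the kind of rule a charter would hold. This stands as a limit: a reader might infer that the sponsor has no plan for such lesions, but only the visible text can be judged.

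**The direction is not guaranteed.** A treated lesion read as non-evaluable would drop out of the paired sum (SAP 3.5.2), and a patient whose volume cannot be calculated is a non-responder (SAP 3.5.1). This also stands. Inflation arises only when the lesion is still measured and read as smaller.

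**The size is hypothetical.** No affected patient is documented, every illustrated rate lies inside its starting interval, and the analysis is descriptive. All true. But the interval describes sampling error; it does not say whether a response was assisted by a procedure.

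**The windows contradict each other.** A reader might infer this from Table 3-1, SAP section 2 and the phrase "at 24 weeks (i.e., ± 4 weeks) following the index date" in SAP 3.3. The documents do not support it. SAP 3.3 says that the plus-or-minus 4 weeks shorthand takes in 24 weeks or 6 months, with 6 months set at week 27. Then 27 + 4 = week 31, and all of week 31 lies inside 20 to under 32. At most the phrase needs rewording.

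**Conclusion.** The concern holds for the visible text, as a gap in supportive analysis and not as an error in the primary definition. Only rescue surgery from index to 24 weeks prevents a response. Up to about 32 of 56 weeks between scans can lie outside that rule, non-rescue procedures are not excluded at any time, and no visible analysis relates procedures between the scans to response. Each affected responder is worth 2.0 points at n=50. This rests on the treated lesion still being read as a volume loss and on no rule in the unseen Charter, manual or redacted text already removing it.

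It would be going too far to read the 57% as a share of responses in doubt, or to say that the response rate is inflated. The first is elapsed time for an extreme scan pair. The second needs a count that the documents do not give and that may be zero.

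**What to change.** Leave the primary definition and analysis unchanged. In SAP 3.5.3:

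1. **Count.** Report, by response status, the number of evaluable patients with a volume-reducing PROS procedure dated between the two scans actually used: debulking, vascular surgery, amputation, sclerotherapy, endovascular occlusion, and laser where recorded. Show procedures at a target-lesion site separately from those with no recorded site. Do not flag surgery recorded at a non-target site. State how many flags rest on an imputed date: Tables 4-1 and 4-3 can move a partly dated procedure from before index to index or later, and so into the scan interval.
2. **One sensitivity analysis.** Count responders with a target-site procedure as non-responders, with the Clopper-Pearson 95% CI. Repeat with site-unknown procedures included, as the conservative bound. The repeat matters because Protocol 6.3.2 names an intended site for surgeries but not for sclerotherapy or occlusion. Patients without a Week 24 scan keep their primary classification.

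Optionally, reword the plus-or-minus 4 weeks phrase in SAP 3.3 to match Table 3-1.

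Cost: one extra table, from data mostly already named for abstraction (laser is not among the examples). The downside is a figure that may be conservative, because some flagged patients would have responded anyway.

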### Definition of response

Patients included in the analysis population for the primary endpoint will be defined as responders if they meet all of the following criteria:

- Patient achieved  $\geq 20\%$  reduction from index date (or up to 12 weeks prior) in the sum of target lesion volumes (1 to 3 lesions, via central radiological assessment) by the change between the index date and 24 weeks (+/- 4 weeks) following the index date
- None of the individual target lesions has  $\geq 20\%$  increase from index date to Week 24 (+/- 4 weeks)
- Patient did not permanently discontinue alpelisib prior to 24 weeks of treatment
- Patient did not require surgery as rescue therapy between index date and 24 weeks of treatment with alpelisib due to disease deterioration.
- No progression of non-target lesions at Week 24 (+/- 4 weeks)
- No appearance of new lesion at Week 24 (+/- 4 weeks)

Patients will be considered as having a missing response if volume assessment at 24 weeks (+/- 4 weeks) following the index date was not performed and:

- Patient did not permanently discontinue alpelisib prior to 24 weeks of treatment
- Patient did not require surgery as rescue therapy between index date and 24 weeks of treatment with alpelisib due to disease deterioration.

Patients will be defined as non-responders in all other cases. In particular, patients with MRI scan performed at Week 24 (+/- 4 weeks) for which the volumetric measurement of the selected target lesions (1 to 3 lesions, via central radiological assessment) cannot be calculated will be considered as non-responders.

Disease progression at any assessment is defined as an increase of any individual target lesions of  $\geq 20\%$  in volume from previous assessment, progression of non-target PROS lesions or appearance of a new PROS lesion.

Relative to non-target lesions, progression will be assessed for the lesions that are identified at index date (or up to 12 weeks prior) with available information at Week 24 (+/- 4 weeks) and new lesions. At Week 24 the central imaging reviewer will make a conclusion if overall level of non-target disease burden decreased or increased unequivocally.

All patients in the efficacy population without a missing response will be used for the primary analysis of the primary endpoint (complete case analysis).

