The volume of the target and all other measurable non-target lesion(s) will be assessed by a central imaging vendor and the details of this review will be captured in the Independent Central Review Charter. All available MRI scans, CT scans, and photographs will be shared with the vendor for assessment. Target lesions for the analysis of study endpoints will be independently selected by the central imaging reviewer using available images from up to 24 weeks prior to the index date, prior to any assessment of images from later in the study period. Central reviewers will take into consideration the clinical impact of the lesions.

Definition of target lesion

In the medical record, it is anticipated that measurable target lesions have already been selected by the treating physician based on the clinical/functional impact of such lesions. The clinical/functional impact will be associated with at least one of the following: patient's complaints, clinical symptoms, impaired organ function, functional limitations affecting patient's everyday life.

However, the target lesions will be independently selected by the central imaging reviewer using pre-index date scans and clinical information regarding symptoms provided by the investigator. More details can be found in the Central Imaging Site Manual.

In addition to the above, the target lesion may be:

- Anatomically reproducibly defined tissue(s) masses, composed of one or several tissue types
- Accurately measurable by imaging technique, MRI or other imaging modality
- Identified at index date and ideally its size would be at least 2 cm in longest diameter at the index date (for each selected lesion)

Target lesions will be determined by the local investigator and shared with the central reviewer using available images from index date prior to any assessment of images from later in the study period. If the central review team disagrees with the local investigator's target lesion selection, adjudication will occur.

Definition of non-target lesion

The non-target lesion consists of all other PROS-related anatomic lesions and may include the following:

- All anatomic lesions other than selected as target and may be measured at radiologic assessment (including small lesions less than 2 cm on MRI)
- Anatomic lesions, limb/truncal areas affected by PROS, organomegaly when they may be measured only by caliper/ruler (e.g., circumference of changed limb or body part)

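### SAP 3.5.1 lets a patient with observed progression or a new lesion but no Week-24 target volume be both non-responder and missing, and its unmeasurable-scan rule covers only MRI

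*SAP*

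**What the plan says.** SAP 3.5.1 introduces seven criteria with "Patients will be defined as non-responders if they meet at least one of the following criteria". They include progression of non-target lesions, a new lesion, and a Week-24 MRI that yields no target volume. On the source of the first two the section says: "Progression based on non-target and new lesions will be based on radiological assessment of the central reader".

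The same section calls the response missing if "lesion volume(s) assessment at 24 weeks or 6 months (+/- 4 weeks) following the index date is not available", provided that the patient neither stopped alpelisib before 24 weeks nor needed rescue surgery. Patients with a missing response are left out of the primary complete-case analysis.

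SAP 3.5 settles one case: patients "with MRI scan performed at Week 24 or 6 months for which the volumetric measurement cannot be calculated are defined as non-responders".

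Protocol 6.8.1 words the missing rule differently: "volume assessment at 24 weeks (+/- 4 weeks) following the index date was not performed". It has the same two exceptions and then places everyone not otherwise classed among the non-responders. The SAP does not carry over that residual rule. The MRI-only wording comes from the protocol, which refers to "patients with MRI scan performed at Week 24 (+/- 4 weeks) for which the volumetric measurement of the selected target lesions" that cannot be calculated. Yet the target-lesion definition in SAP 1.3 reads "Accurately measurable by imaging technique, MRI or other imaging modality", and the same section sends CT scans to the central vendor.

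SAP section 2, which lists changes to the protocol analysis, mentions only the time windows.

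**The concern.** The missing-response rule fixes the denominator of the primary estimate. Where two definitions apply to one patient and neither has priority, the programmer decides whether an observed failure counts as a failure or disappears. The error has one direction: removing a patient who cannot be a responder never lowers the rate, and raises it whenever there is at least one responder.

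The choice carries into Sensitivity Analysis 2. If such a patient is classed as missing, the best-case arm counts as a responder someone whose new lesion or progression already rules out response under 3.5.1.

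The MRI-only wording raises a related question. The same gap in evidence, target lesions imaged but not measurable, has opposite consequences by modality, and the documents give no reason for this.

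**Working it through.** **Plan's own figure.** Clopper-Pearson 95% limits for 10, 15, 20 and 25 responders of 50 reproduce protocol Table 6-2: 0.100–0.337, 0.179–0.446, 0.264–0.548 and 0.355–0.645. The tabulated widths are 0.237 to 0.289.

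**Logic check.** Take a patient with no Week-24 target volume, no early discontinuation and no rescue surgery. Three yes/no facts remain: non-target progression, new lesion, and a Week-24 MRI from which the volume cannot be calculated. That gives 2 × 2 × 2 = 8 combinations.

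- All 8 meet the SAP missing rule.
- 7 of the 8 also meet a non-responder criterion.
- 4 of those 7 include an uncalculable MRI, which SAP 3.5 assigns to non-response.
- The other 3 (progression, new lesion, or both, without such an MRI) are unresolved.

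The paired-lesion rule in SAP 3.5.2 narrows this further: if only some target lesions lack a Week-24 volume, the sum uses the others. The overlap therefore needs every target volume to be absent. The unresolved patients are mainly those assessed by another modality or whose target lesions were not imaged.

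**Modality check.** An unreadable CT of the target lesions, with no progression or new lesion, meets only the missing rule. The same finding on MRI is a non-response.

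**Size.** Inputs: n = 50 (protocol 6.6) and the Table 6-2 rates. The number of affected patients u is an assumption, set at 1 or 2, with no other missing responses. With x responders and p = x/n:

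- classed as non-responders: x/n
- classed as missing: x/(n − u)
- shift: x/(n − u) − x/n = p·u/(n − u)

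| Responders | As non-responders | u = 1 missing | u = 2 missing |
|---|---|---|---|
| 10 | 10/50 = 20.0% | 10/49 = 20.4% | 10/48 = 20.8% |
| 15 | 15/50 = 30.0% | 15/49 = 30.6% | 15/48 = 31.3% |
| 20 | 20/50 = 40.0% (26.4–54.8) | 20/49 = 40.8% (27.0–55.8) | 20/48 = 41.7% (27.6–56.8) |
| 25 | 25/50 = 50.0% | 25/49 = 51.0% | 25/48 = 52.1% |

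Smallest shift: 0.2 × 1/49 = 0.41 points. Largest: 0.5 × 2/48 = 2.08 points.

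**Sensitivity Analysis 2, 20 responders.** The worst-case arm returns 20/50 = 40.0%. The best-case arm gives 21/50 = 42.0% (28.2–56.8) or 22/50 = 44.0% (30.0–58.7), although none of the added patients with progression or a new lesion can be a responder under 3.5.1.

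**The case against.** The strongest reply is that the conflict may be empty in practice. The patient needs no Week-24 MRI that brings SAP 3.5 into play, no measurable target lesion, continued treatment, no rescue surgery, and a failure seen by the central reader on some other image. The duration-of-response text in SAP 3.6 ties volumetry to MRI, and nothing shows that such a patient exists. SAP 3.5.2 also requires reasons for missing responses to be reported where available, and the worst-case arm counts these patients as failures. All of this stands, and it limits the size. It does not say which definition wins, and a sensitivity bound does not correct the primary estimate.

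It can also be said that a best-case arm is extreme by design. That is fair for unknown outcomes; here a failure has been observed.

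A reader might infer that Sensitivity Analysis 1 is affected too, because it imputes target volumes and does not mention observed failures. The documents do not support this. Response status has to be determined after imputation, and the responder list in 3.5.1 requires no non-target progression and no new lesion. If that list is applied, an observed failure blocks response whatever volume is imputed.

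Finally, SAP 3.5.1 refers to the Independent Central Review Charter for details of radiographic evaluation. The Charter was not available and may contain evaluability rules. The analysis class of missing response is nevertheless defined in the SAP and should be unambiguous there.

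**Conclusion.** The point holds in a limited form. SAP 3.5.1 has two definitions that can apply to the same patient, with no precedence, and a criterion that treats unreadable scans differently by modality. The possible bias in the primary rate is upward only. It is small under the stated assumption of one or two patients among 50 and no other missing responses: 0.4 to 2.1 points, in a descriptive analysis without hypothesis tests.

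A reader might infer that the SAP quietly loosened the protocol. That is only partly shown. The SAP did change the trigger wording and did not carry over the residual rule, and section 2 declares neither. But read literally, the protocol also makes the response missing when the target lesions were not imaged, even with a new lesion elsewhere. The MRI-only wording is inherited. Whether an unreadable CT is handled differently from the protocol depends on whether a performed volume assessment means the scan or the volume, which the protocol does not say.

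Severity: minor. Confidence: moderate, because the number affected is unknown and the Charter was not seen.

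**What to change.** 1. In SAP 3.5.1, state that any observed non-responder criterion takes precedence, and that response is missing only if the target lesions were not imaged in the Week-24 window and no non-responder criterion is met. For patients whose targets were not imaged, acknowledge that this is a new rule relative to the literal protocol. The best-case arm then no longer includes observed failures.
2. In SAP 3.5 and 3.5.1, replace the reference to an MRI scan with imaging of the selected target lesions, by MRI or another modality. Define an uncalculable volume as one where no selected target lesion is measurable, so that the criterion agrees with the paired-lesion rule in 3.5.2. Naming the target lesions matters: a criterion covering any imaging scan would turn a CT of another body region into a non-response. It also means that a Week-24 MRI that missed the targets, a failure under a literal reading now, becomes missing unless another failure criterion is met.
3. List these changes in SAP section 2 and check them against the Independent Central Review Charter.

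The cost is a few sentences and the matching derivation, with no new data or tables. The downside is that the reported rate may be slightly lower.
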